Appendix C: Patient Post-Education Patient Survey

Participant Name: _____

Participant Study ID: _____

Date: _____

Thank you again for taking part in our educational intervention. Before the session is over, we hope to get your feedback on the session so that we can continue to improve on our education of patients on germline testing.

Section A:

Please answer these questions as True or False.

		True	False
1.	Genes are made from pieces of DNA		
2.	A mutation is a change in DNA sequence		
3.	Cancer is caused by a combination of inheritance, environmental exposure, and lifestyle factors		
4.	Most people who develop cancer do so because they have inherited risk for cancer that they were born with.		
5.	All of the gene mutations that could increase risk for cancer have been discovered.		

Section B

Please answer these questions with agree, disagree, or if you are unsure, "I don't know".

		Agree	Disagree	I don't know
1.	Some men with prostate cancer were born with genetic mutations which contributed to their development of cancer.			
2.	Knowing about inherited risk (passed down within a family) can affect choices about cancer treatments (for example, medications or surgery).			
3.	People with an inherited risk for cancer (and their at-risk relatives) are more likely to develop more than one type of cancer.			
4.	The blood relatives (for example, sister, father, or child) of a person with a mutation in a cancer risk gene might share the same gene mutation.			
5.	A person with an inherited risk for cancer may have distant relatives (for example, cousins) who also have increased cancer risk.			

6.	All children of a person with inherited cancer risk will also have inherited cancer risk.			
----	---	--	--	--

Section C

The following questions are about the extent of your interest in genetic testing for your cancer.

- How interested are you in undergoing genetic testing to determine if you were born with any genetic mutations which predisposed you to developing prostate cancer?
 - F. Very interested
 - G. Interested
 - H. Neutral
 - I. Not interested
 - J. Not at all interested
- Of the following listed factors, which would **most** influence you in a decision to pursue germline DNA testing in the care of your cancer? (**Rank answers in orders of preference from 1 to 5, 1= best describes, 5= least describes**)

	Rank (1 = best, 5 = least)
Potential to guide treatment selection	
Potential to predict disease outcome	
Potential to learn more about my cancer risk	
Potential to learn more about the cancer risk of my family	
Trust in my physician and their recommendation for genetic testing	
Other (please specify; not required)	

- Of the following listed factors, which would **most** influence you in a decision to **not** pursue genetic DNA testing in the care of your cancer? (**Rank answers in orders of preference from 1 to 5, 1= best describes, 5= least describes**)

	Rank (1 = best, 5 = worst)
Potential of DNA test results to be of no clinical value	
Potential of DNA test results to lead to health, life or disability insurance discrimination	

Concerns about the privacy and confidentiality of DNA test results	
Concerns about the impact a positive result would have on my family and relatives.	
Other (please specify; not required)	

Section D

For each statement, please select if you ‘Disagree Strongly’, ‘Disagree’, ‘Neither Agree or Disagree’, ‘Agree’ or ‘Agree Strongly’.

		Disagree strongly	Disagree	Neither Agree or Disagree	Agree	Agree Strongly
1.	The information presented in this session was informative .					
2.	The information presented in the session was confusing or difficult to understand .					
3.	The information presented in the session was distressing .					
4.	The information presented in the session was useful .					
5.	The information presented in the session answered all of my questions and concerns .					
6.	The session was the right length of time .					
1.	The pamphlet was helpful in explaining the concept of genetic testing.					

2. For question #6, if you answered **disagree to disagree strongly**, please tell us whether your education session was:
 - A) Too long
 - B) Too short
3. For question #7, if you answered **disagree to disagree strongly**, please tell us whether the pamphlet was:

- A) Too basic
- B) Too advanced
- C) Other (*please specify*): _____

4. At the end of this educational session, my decision on pursuing genetic testing is:

- A) I want to proceed with germline testing done today.
- B) I do not want to proceed with germline testing today.
- C) I would like to see a genetic counsellor to discuss this further.
- D) I am unsure and will decide at a later date.

If you have any other comments about the educational intervention, please feel free to share below:

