The patient will then have an opportunity to ask questions. If a patient wishes to proceed with testing, they will sign the standard consent to proceed with germline testing and the patient's clinician will be notified of intent to proceed with germline testing. Patients can elect to decline testing, defer testing to a later time, or request referral to genetic counseling to discuss the testing. We will track patterns of patient decision making following the educational intervention. Upon a patient deciding to pursue testing, testing will consist of a prostate cancer germline panel with a commercially available blood or saliva-based assay. Following the educational intervention, the patient will be asked to complete a short patient education and satisfaction questionnaire (Appendix D). Upon receipt of the results, the coordinator will alert the patient's clinician, who will then share the results with the patient either in clinic or by phone. If the results show a

pathogenic germline mutation, the patient will be referred to see the UCSD cancer medical genetics clinic for consultation with a genetics counselor. Additionally, the patient can elect to see a genetics counselor independent of the test results once the test results are reviewed. If a patient pursues genetic testing, following receipt of results, the patient's clinicians will be asked to complete a short survey on to assess how the results of germline testing affected the patient's current and future management (appendix D). There will be capacity for patients to complete questionnaires electronically. Additionally, to systematically understand the scope of questions asked by patients which will provide opportunity to optimize the educational intervention, we will record the educational sessions.

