3.5 Participant Follow-up

Patients will be followed for 24 months following the educational session. We will capture deferred decisions to pursue germline testing during the 24-month follow up period. Data on oncologic outcomes, prostate cancer management, and cancer surveillance will be obtained from the medical record.

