 - Not at all interested
- Of the following listed factors, which would **most** influence you in a decision to pursue germline DNA testing in the care of your cancer? (**Rank answers in orders of preference from 1 to 5, 1= best describes, 5= least describes**)

	Rank (1 = best, 5 = least)
Potential to guide treatment selection	
Potential to predict disease outcome	
Potential to learn more about my cancer risk	
Potential to learn more about the cancer risk of my family	
Trust in my physician and their recommendation for genetic testing	
Other (please specify; not required)	

3. Of the following listed factors, which would **most** influence you in a decision to **not** pursue genetic DNA testing in the care of your cancer? (**Rank answers in orders of preference from 1 to 5, 1= best describes, 5= least describes**)

	Rank (1 = best, 5 = worst)
Potential of DNA test results to be of no clinical value	
Potential of DNA test results to lead to health, life or disability insurance discrimination	
Concerns about the privacy and confidentiality of DNA test results	
Concerns about the impact a positive result would have on my family and relatives.	
Other (please specify; not required)	

4. At the start of this educational session, my current decision on pursuing genetic testing is:

- A) I want to proceed with germline testing done today.
- B) I do not want to proceed with germline testing today.
- C) I am unsure at this time.

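### The end-of-session decision question puts men who refuse testing and men who want it on a later day in the same answer box

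*Combined protocol and SAP*

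**What the plan says.** Section 3.1 sets out what a man may do after the session if he does not go straight to testing: "Patients can elect to decline testing, defer testing to a later time, or request referral to genetic counseling to discuss the testing". It continues: "We will track patterns of patient decision making following the educational intervention". Section 3.5 adds: "We will capture deferred decisions to pursue germline testing during the 24-month follow up period".

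The decision itself is asked in Appendix C, Section D, in the question numbered 4 that follows the satisfaction statements. It has four answers:

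- The first accepts, and ties acceptance to the day of the session: "A) I want to proceed with germline testing done today".
- The second turns testing down, again only for that day: "B) I do not want to proceed with germline testing today".
- The third is for men who first want counselling: "C) I would like to see a genetic counsellor to discuss this further".
- The fourth is for men who have not made up their minds: "D) I am unsure and will decide at a later date".

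Appendix A, Section C item 4 asks the same thing before the session. It has the same first two answers and a single third one: "C) I am unsure at this time".

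Neither section 3.1 nor section 3.5 names the form that supplies the tracked decisions, and nothing in sections 4.2 to 4.5 says how a decline or a deferral is to be coded.

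**The concern.** Both the accepting and the declining answer are tied to the day of the session. A man who has made up his mind to be tested, but on another day, cannot tick A. He is not unsure, so D is wrong for him, and he may have no wish for counselling, so C is wrong too. That leaves B, which is also the only box open to a man who does not want testing at all.

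The two answers mean different things to a pilot of an education programme. Refusal after the session suggests that the education did not persuade. Deferral suggests that timing or logistics stood in the way. A report on how men decided after education would want to tell them apart, and intent at the session is hard to recover later.

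**Working it through.** **The plan's own figure.** Sections 4.5.1 and 4.8 give a 95% confidence interval width of 0.27 to 0.29 for n = 50 and observed proportions from 0.3 to 0.7, by the exact method. The exact limits are the 0.025 quantile of Beta(x, n − x + 1) and the 0.975 quantile of Beta(x + 1, n − x):

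- x = 15: 0.1786 to 0.4461, width 0.2675 (the same width at x = 35)
- x = 20: 0.2641 to 0.5482, width 0.2841 (the same width at x = 30)
- x = 25: 0.3553 to 0.6447, width 0.2895

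The statement reproduces. It concerns completed testing and does not use the survey answer.

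**Decisions against boxes.**

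| Decision at the end of the session | Box that fits | Shared with |
|---|---|---|
| Wants testing the same day | A | – |
| Wants testing, on a later day | B | men who refuse |
| Does not want testing | B | men who want it later |
| Wants to see a counsellor first | C | – |
| Undecided | D | – |

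Only the second and third rows collide.

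**What the question alone can bound.** The documents give no expected counts, so those below are assumed. With b men in B, d in D and n = 50, refusal lies between 0 and b/n. Deferral, counting the undecided men, lies between d/n and (b + d)/n.

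| b | d | Refusal | Deferral |
|---|---|---|---|
| 5 | 5 | 0 to 5/50 = 0 to 10% | 5/50 to 10/50 = 10 to 20% |
| 10 | 5 | 0 to 10/50 = 0 to 20% | 5/50 to 15/50 = 10 to 30% |
| 15 | 5 | 0 to 15/50 = 0 to 30% | 5/50 to 20/50 = 10 to 40% |

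For b = 10 the two extremes have exact 95% intervals of 0 to 7.1% (0/50) and 10.0 to 33.7% (10/50).

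**What follow-up adds.** Suppose 4 of those 10 men are tested later (again assumed). They are known to have tested. The other 10 − 4 = 6 could hold anywhere from 0 to 6 refusers, that is 0 to 6/50 = 12% of the cohort. Among the 4, a planned deferral and a refusal later reversed look alike. Under the milestones, accrual starts in October 2021 and the database locks in October 2022 or sooner. No man can therefore have 24 months of follow-up at that lock, and part of this later information would not yet be available.

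**Other possible sources.** Section 3.1.1 lists demographics, clinical and disease characteristics and questionnaire results. Section 4.3 lists no testing-decision variable. After the session, the schedule in section 5.1.1 has only the results review and the clinician questionnaire. The signed testing consent in section 3.1 identifies men who accept; it does not divide those who do not.

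**The case against.** A good deal can be said for the form as it stands.

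- **Two groups are already separated.** Undecided men have D and men who want counselling have C. This stands, and it narrows the problem to men who have decided to be tested on another day.
- **The tracking is not tied to this question.** A coordinator sits with each man, the sessions are recorded, and the decision could be noted elsewhere. So a reader who infers that decline and deferral counts cannot be obtained at all goes further than the documents allow. What remains is that no other source or rule is stated. The stated purpose of the recordings is to catalogue patients' questions.
- **Follow-up covers everyone.** Section 3.5 follows all enrolled men, so nobody has to be labelled a deferrer to have later testing captured. This stands. It leaves unresolved the men in B who meant to be tested and never were.
- **There is a proxy on the same form.** Appendix C, Section C item 1 grades interest in testing after the session. A man in B who is very interested differs from one who is not at all interested. This helps, but interest is not a decision and no rule combines the two answers.
- **No endpoint is a decline or deferral count.** Section 4.2 lists none. This stands and limits the consequence.

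A reader might also infer that video and telephone participants are affected more, because they may be unable to give a sample the same day. The documents do not say how remote men provide one, and they allow a saliva assay, so that differential effect is unsupported.

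**Conclusion.** The point holds in a limited form. Answer B merges refusal with a settled wish to be tested on another day, section 3.1 treats these as different decisions to be tracked, and the plan states no other source or coding rule for separating them. The 24-month follow-up resolves part of B, not all of it.

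The size depends on how many men tick B, which the documents do not predict. On the question alone, the range for refusal is as wide as B itself: 10 to 30 percentage points for 5 to 15 of 50 men.

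The consequence is descriptive only. It touches the account of decision patterns and any before/after comparison of this question within the opinion results. By item count the decision question is not one of the 14 repeated items in section 5.1.2: the repeated items are 5 + 6 + 3 = 14 in Sections A to C of Appendix C, and the decision question is among the other 10. It is nevertheless asked on both forms, so such a comparison is a natural one to make.

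It would be wrong to infer that the effectiveness result is at risk. The primary endpoint counts completed tests, and the precision statement for 50 men reproduces and does not depend on this answer.

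**What to change.** In Appendix C, Section D, the decision question, replace B with two answers: *I do not want germline testing* and *I want germline testing, but not today*. Keep the counsellor and unsure answers as separate boxes. Men who want testing later should not be pooled with undecided men, whom the present form already keeps apart.

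Make the same split in Appendix A, Section C item 4, so that answers before and after the session stay comparable.

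Add one sentence to section 3.1 or 4.5.2 saying that these answers supply the decline and defer counts.

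If surveys have already been collected, record the form version and report B answers from the present form as not today, reason unspecified.

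The cost is a minor amendment to two survey items and the matching REDCap fields, with no meaningful extra patient time. The drawback is two form versions to report if collection has begun.

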Appendix D: Post Results Clinician Questionnaire

Clinician Name: _____ Date: _____

Patient/Patient Study ID: _____

1. Did you find the germline test result helpful in the management of this patient?

- A) Yes
- B) No
- C) Unsure

2. Did the results of germline testing change your management of this patient currently?

- A) Yes
- B) No
- C) Unsure

3. Will the results of the testing change your management of this patient in the future?

- A) Yes
- B) No
- C) Unsure

4. Did the results of this testing change your perception of the patient's prognosis?

- A) Yes
- B) No
- C) Unsure

5. Did the results of this testing lead to further diagnostic testing or referrals?

- A) Yes
- B) No
- C) Unsure

6. If you have any additional feedback about the results or educational intervention with regards to this patient's case, please feel free to share:

Appendix E: List of genes tested with commercial germline assays

Ambry Panel

1. ATM
2. BRCA1
3. BRCA2
4. CHEK2
5. EPCAM
6. HOXB13
7. MLH1
8. MSH2
9. MSH6
10. NBN
11. PALB2
12. PMS2
13. RAD51D
14. TP53

Invitae Panel

1. ATM
2. BRCA1
3. BRCA2
4. BRIP1
5. CHEK2
6. EPCAM
7. FANCA
8. GEN1
9. HOXB13
10. MLH1
11. MSH2
12. MSH6
13. NBN
14. PALB2
15. PMS2
16. RAD51C
17. RAD51D
18. TP53

ATTACHMENTS

See attached file of educational brochure brochure.

